10.2.1. Event-free survival

EFS is assessed by investigator based on modified International Working Group (IWG) AML response criteria (Section 17.4).

Event-free survival (EFS) is defined as the interval from either the date of the first dose for subjects in Phase 1b or the date of randomization for subjects in Phase 2 to the date of documented morphologic relapse, progression, or death from any cause, whichever occurs first. Censoring rules are provided in Table 4. The analysis of the EFS for Phase 2 will be conducted using the log-rank test in the ITT population, and mITT population. The Cox proportional hazards regression model will be used to estimate the hazard ratio and the corresponding 95% confidence interval for oral AG-221 with SC azacitidine relative to SC azacitidine alone.

Additionally, the number of events, the number of censored and reasons for censoring will be summarized (n, percent) for this endpoint. KM curves will be provided by treatment arm in figures.

Table 4: Censoring Rules for EFS

Value of Event-free Survival Date (ADT)	Censored (Y, N)	Derivation
ADT = min(death date, MR date, progression date)	N	If a subject died, had MR, or had disease progression by investigator review, and the subject has less than two consecutive missing response assessments prior to a visit documented death, MR, or progression which is before new AML therapy
ADT = the last event-free assessment date before missing assessments/ randomization date	Y	If a subject died, had MR, or had disease progression by investigator review, and the subject has two or more consecutive missing response assessments prior to a visit documented death, MR, or progression
ADT = the last adequate assessment date/randomization date	Y	If a subject did not die, did not have MR, or did not have progression, and did not receive any subsequent anticancer therapy. If there was no post-baseline response assessment, then ADT = the randomization date.
ADT = the last adequate assessment date on or prior to start of subsequent anticancer therapy/randomization date	Y	If a subject did not die, did not have MR, or did not have progression on or prior to start of subsequent anticancer therapy. If there was no post-baseline response assessment, then ADT = the randomization date.
ADT = the last adequate assessment date on or prior to start of subsequent anticancer therapy/randomization date	Y	If a subject died, had MR, or had disease progression by investigator review after receiving subsequent anticancer therapy. If there was no post-baseline response assessment on or prior to start of subsequent anticancer therapy, then ADT = the randomization date.

ADT = analysis date; N=no; Y= yes, MR=morphologic relapse.

Note: Event-free response refers to a response that was neither morphologic relapse(MR), progressive disease (PD) nor death.

Sensitivity analyses for EFS will be done with the following censoring rules:

- Subjects with two or more consecutive missing response assessments prior to an event date (death, MR or disease progression) will be considered as events at the event date by ignoring the missing assessments; (EFS1)

- Subjects with subsequent AML therapy prior to an event date will be considered as events at the event date; (EFS2)
- Analysis of EFS with subjects censored at the time of transplantation after study treatments; (EFS3)

Other sensitivity rules may be added when data is available.

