**Table 2: Study Endpoints (Continued)**

Endpoint	Name	Description	Timeframe
Primary	Overall Response Rate (as assessed by the investigator)	Rate of CR + CRi + CRp + MLFS + PR according to modified IWG AML response criteria ( Appendix F ).	Approximately 30 months
Secondary	Event-Free Survival	Time from randomization to documented morphologic relapse, progression according to modified IWG AML response criteria ( Appendix F ), or death from any cause, whichever occurs first.	Approximately 30 months
	Safety / tolerability	Type, frequency, seriousness and severity of AEs, and relationship of AEs to study treatment.	Approximately 30 months
	Complete remission rate	Rate of CR according to modified IWG AML response criteria ( Appendix F ).	Approximately 30 months
	Sponsor Derived CR	Rate of CR based on laboratory data	Approximately 30 months
	Sponsor Derived CR and CRh	Rate of CR +CRh based on laboratory data	Approximately 30 months
	Hematologic improvement rate	Rate of HI-N + HI-P + HI-E according to IWG MDS HI criteria ( Appendix G ).	Approximately 30 months
	Duration of Response	Time from the first documented MLFS/CR/CRi/CRp/PR to documented morphologic relapse, progression according to modified IWG AML response criteria ( Appendix F ), or death due to any cause, whichever occurs first	Approximately 30 months
	Time to response	Time from first dose of study drug to first documented CR/CRi/CRp/MLFS/PR according to modified IWG AML response criteria ( Appendix F )	Approximately 30 months
	Time to sponsored assessed CR and CRh	Time from first dose of study drug to first documented CR / CRh	Approximately 30 months
	Duration of sponsor assessed CR and CRh	Time from the first documented CR/CRh to documented morphologic relapse, progression	Approximately 30 months
Overall Survival	Time from randomization to death due to any cause.	Approximately 30 months	

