## 9. STATISTICAL CONSIDERATIONS

The sections below provide an overview of the proposed statistical considerations and analyses. The final statistical analysis methods will be documented in detail in the statistical analysis plan (SAP).

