##### **9.6.2. Phase 2 AG-221 Randomized Stage**

For subjects in Phase 2, response will be primarily assessed by investigator review.

All efficacy analysis will be performed in the ITT population. Key efficacy analysis will also be performed on the mITT and EAP as supportive evidence and to assess the robustness of the efficacy findings. Subjects will be analyzed according to randomized treatment group.

The primary efficacy endpoint ORR is defined as the rate of responses including CR, CRi, CRp, MLFS and PR that are assessed by investigator according to modified IWG AML response criteria. The ORR will be summarized by treatment group. The treatment difference in ORR will be tested using the Chi squared test at a two-side 0.2 level and in the ITT population. This test will provide the pivotal p-value for the comparison of the ORR of the oral AG-221 + SC azacitidine versus azacitidine mono therapy. Estimated response rate with 80% and 95% confidence intervals will also be provided.

**Event-free survival (EFS)** is defined as the interval from the date of randomization to the date of documented morphologic relapse, progression, or death from any cause, whichever occurs first. The analysis of the **EFS** will be conducted using the log-rank test in the ITT population. This test will be used for the comparison of the two EFS curves of oral AG-221+ SC azacitidine versus azacitidine mono therapy. The Cox proportional hazards regression model will be used to estimate the hazard ratio and a 95% confidence interval for the hazard ratio.

**Duration of response** is defined as time from the first documented CR/CRi/CRp/MLFS/PR to the date of the first documented morphologic relapse, progression according to modified IWG AML response criteria ([Appendix F](#)), or death due to any cause, whichever occurs first. Subjects without morphologic relapse, progression, or death due to any cause will be censored at the date of the last response assessment. Duration of response will be assessed using Kaplan-Meier methods. Point estimates and 95% CIs will be provided where appropriate for the median and other quantiles.

**Time to response** is defined as time from the date of first dose to the date of first occurrence of response, which includes CR, CRi, CRp, PR and MLFS as determined by investigator. Time to response will be summarized using descriptive statistics in subjects with documented CR, CRi, CRp, PR and MLFS as determined by the investigator.

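### No listed EFS analysis lifts both SAP Table 4 rules that censor recorded events, so the EFS that the protocol defines is not estimated

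*SAP*

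**What the plan says.** The protocol defines EFS twice. Table 2 has "Time from randomization to documented morphologic relapse, progression according to modified IWG AML response criteria", or death from any cause. Section 9.6.2 has "the interval from the date of randomization to the date of documented morphologic relapse, progression, or death from any cause". The definition sentence in SAP 10.2.1 says the same for Phase 2. None of the three makes an exception for missed visits or later treatment.

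SAP Table 4 sets the censoring:

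- Row 1 counts an event only if fewer than two consecutive assessments are missing "prior to a visit documented death, MR, or progression which is before new AML therapy".
- Row 2 censors: "If a subject died, had MR, or had disease progression by investigator review, and the subject has two or more consecutive missing response assessments" before it. The date goes back to the last event-free assessment before the gap, or to randomisation.
- Row 5 censors: "If a subject died, had MR, or had disease progression by investigator review after receiving subsequent anticancer therapy". The date goes back to the last adequate assessment on or before the start of that therapy, or to randomisation.

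Three sensitivity analyses follow. In EFS1, subjects with two or more missed assessments "will be considered as events at the event date by ignoring the missing assessments; (EFS1"). EFS2 counts subjects with subsequent AML therapy before an event as events on the event date. EFS3 censors at transplantation. A closing sentence allows further rules but names none. The section also commits to a report in which "the number of events, the number of censored and reasons for censoring will be summarized (n, percent) for this endpoint".

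**The concern.** EFS is the first-listed secondary endpoint, and the Protocol Summary gives ORR and EFS as what Phase 2 is meant to assess. Under Protocol 6.3, survival is followed every 4 weeks whether or not a marrow is done. The data for EFS as defined will therefore exist, but no hazard ratio that uses all of them is planned. The censoring table will show how many recorded events were set aside and why. It will not show the estimate with those events counted.

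The trial is open-label, so changing therapy or missing marrows could depend on arm or prognosis, and the censoring could then be informative. An analysis free of both rules is the direct check on that.

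The therapy wording adds a smaller problem. Row 1 and EFS2 refer to AML therapy, while rows 4 and 5 refer to anticancer therapy. SAP 8.4.3 uses the latter heading to cover AML and non-AML treatment alike.

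**Working it through.** **1. Recorded events classified by what preceded them.** The rules come from SAP 10.2.1. The plan states no figure to reproduce, so this step is a logic check.

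| Before the recorded event | Protocol definition | Table 4 | EFS1 | EFS2 | EFS3 |
|---|---|---|---|---|---|
| Neither trigger | event | event | event | event | event, unless transplanted earlier |
| Two or more missed assessments only | event | censored | event | censored | censored |
| AML therapy only | event | censored | censored | event | censored |
| Both | event | censored | unclear | event (literal wording) | censored |

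No analysis column matches the definition column. EFS2 falls short by exactly the missed-only class. EFS1 falls short by the therapy-only class, and by the last row too if row 5 stays in force.

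**2. Therapy terms.** Take a death after non-AML anticancer therapy only, without two missed assessments. It precedes any new AML therapy, so row 1 makes it an event. It follows subsequent anticancer therapy, so row 5 censors it. EFS2, worded for AML therapy, does not resolve this.

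**3. When the missed-assessment rule is met.** Protocol Table 4 footnotes w, x and y place marrows before Cycles 2, 3, 5, 7 and so on. With nominal 28-day cycles and no visit windows, these fall on days 28, 56, 112 and 168 after Day 1. Two consecutive misses are then complete:

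- at day 56 if no marrow was done, and a later death is censored at randomisation;
- 112 − 28 = 84 days after a Cycle 2 marrow;
- 168 − 56 = 112 days after a Cycle 3 marrow, and likewise after later ones.

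The documents do not say how often this will happen.

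**4. Size in a simulation (all rates assumed).** There were 1,500 replicates of 66:33 in each of 12 scenarios: three rate levels, frailty variance 0.5 or 0, and response visits stopping or continuing after a switch. Rates were equal in both arms. Other assumptions were a conditional HR of 0.75, control median 8 months, 40% of first events being deaths, median 6 months from progression to death, and follow-up of 12 to 30 months.

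| Switching / missed marrows | Events lost by Table 4 | Left censored by EFS1 | Left censored by EFS2 |
|---|---|---|---|
| 8% / 4% | 4–6 | 3–4 | about 1 |
| 15% / 8% | 8–11 | 6–8 | about 2 |
| 25% / 12% | 13–18 | 10–13 | 2–3 |

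With both rules lifted there are 61 to 74 events. EFS1 and EFS2 are read here as favourably as possible.

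Table 4 against both rules lifted, with frailty variance 0.5 and visits stopping at a switch:

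- Middle level: 54.4 events, HR 0.791, SE of log HR 0.286, against 62.5, 0.802 and 0.267. SE ratio 0.286/0.267 = 1.07.
- Highest level: 48.2 events, HR 0.779, SE 0.303, against 61.3, 0.800 and 0.270. SE ratio 0.303/0.270 = 1.12.

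Across all scenarios the HR differs by 0.002 to 0.021.

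**5. The comparison that matters: EFS2 against both rules lifted.** Taking SE as proportional to 1/√events, losing 1 of 74 gives √(74/73) = 1.007, and losing 3 of 61 gives √(61/58) = 1.026. The cost is about 1% to 3% in SE.

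**6. A deliberately unfavourable single-arm illustration.** EFS was exponential with mean 14 months, so true 12-month EFS is exp(−12/14) = 0.424. If 5% to 15% of subjects are censored 4 months before their event for missed visits, EFS2 gives 0.437 to 0.468, against 0.423 with both rules lifted. That censoring is tied to the event by construction, so this is an outer case for a curve and says nothing about the hazard ratio.

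**The case against.** The case against is strong on consequence. Protocol Section 9 leaves detailed methods to the SAP, so Table 4 is a permitted choice. Varying one assumption at a time is ordinary practice for sensitivity analyses. Numbers and reasons for censoring will be reported, and OS counts deaths after a switch. EFS has no stated event target or power. Much of what a combined analysis adds will be deaths after a change of therapy. All of this stands, and it limits the point to a minor one. It does not supply the missing estimate, and the open-ended sentence pre-specifies nothing.

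Several stronger readings are tempting, but the documents do not support them:

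- *Table 4 contradicts the protocol.* It narrows the definition, but within what Protocol Section 9 delegates.
- *The censoring biases the comparison.* No rates or direction can be found in the documents. The simulation used equal rates in both arms, so it cannot show such a bias.
- *The missing analysis costs 3% to 15% in standard error.* That range compares Table 4 with both rules lifted. EFS2 already recovers most of it.
- *EFS2 is ambiguous for subjects with both triggers.* Its literal wording covers anyone with subsequent AML therapy before the event and makes no exception for missed visits. Only EFS1 is unclear here.
- *Protocol 6.3 conflicts with 3.1.2.4 on second-line therapy.* Section 6.3 limits response visits to subjects who stopped treatment before relapse, progression or second-line therapy, so the two largely agree. What remains is looser wording in the Protocol Summary, Protocol 3.1 and SAP 4.1, which mention only progression.

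The list could also be read as cumulative, so that EFS2 lifts both rules. The SAP does not say so, and separate labels suggest separate analyses.

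**Conclusion.** The point holds as a cheap, minor improvement. On the text, EFS1 still censors events after new therapy alone, EFS2 still censors events after missed visits alone, and EFS3 lifts neither rule. The conflict between rows 1 and 5 over non-AML therapy is a plain drafting defect, probably affecting few subjects, though the documents give no figure.

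The expected numerical gain over EFS2 is small: about 1 to 3 further events of 61 to 74, with little movement in the hazard ratio. This rests on the assumed switching and missed-marrow rates being about right and equal in the two arms. If missed visits cluster just before events, the absolute EFS curve could shift by more than the hazard ratio does. The main benefit is that the trial would report the endpoint it defined.

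**What to change.** Keep Table 4 as the main analysis and keep EFS1 to EFS3. In SAP 10.2.1:

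- Add EFS4, a supplementary ITT analysis with both rules lifted. Every recorded relapse, progression or death from any cause is an event on its date. Subjects without an event are censored at the last adequate assessment, or at randomisation if there is none. Label it post hoc if EFS has already been reported; the latest protocol amendment's justification describes 24-month EFS data as available.
- Use one defined therapy term in rows 1, 4 and 5 and in EFS2.
- State which Table 4 rows stay in force in EFS1 and in EFS2.
- Count an assessment as missing only if it was due under the protocol schedule and not done.
- Align the Protocol Summary, Protocol 3.1 and SAP 4.1 with Protocol 3.1.2.4 and 6.3 on when response visits end.

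The cost is SAP wording, small protocol text edits and one extra run on data already collected. There is a downside to state alongside EFS4: its added events after a switch will be mostly deaths that partly reflect later therapy. Subjects alive without an event also stay censored at their last assessment while later deaths count. It therefore supplements Table 4 and does not replace it.

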10.2.2. Duration of Response

Duration of response is defined as time from first documented CR/CRi/CRp/PR/MLFS to documented morphologic relapse, PD, or death due to any cause, whichever occurs first. Subjects without morphologic relapse, PD, or death due to any cause will be censored at the date of the last response assessment.

The duration of response will be analyzed using the KM method. The 25th percentile, median and 75th percentile time (including two-sided 95% CI) will be summarized for each treatment arm. Only subjects with documented CR/CRi/CRp/PR/MLFS response as determined by investigator assessment will be included in the analysis.

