17.4. International Working Group Acute Myeloid Leukemia Response Criteria

Hematologic Response According to modified IWG Criteria for AML	
Category	Definition
Morphologic Complete Remission (CR)	Defined as less than 5% blasts in a BM aspirate sample with marrow spicules and with a count of at least 200 nucleated cells. There should be no blasts with Auer rods and absence of extramedullary disease. Plus, all the following conditions should be met: 
 ANC $\geq 1 \times 10^9/L$ (1,000/μL) Platelet count $\geq 100 \times 10^9/L$ (100,000/μL) Independent of red cell transfusions for ≥ 1 week immediately before each response assessment
Morphologic Complete Remission with Incomplete Neutrophil Recovery (CRi)^a	Defined as all criteria of morphologic CR except the following: 
 ANC $< 1 \times 10^9/L$ (1,000/μL)
Morphologic Complete Remission with Incomplete Platelet Recovery (CRp)^a	Defined as all criteria of morphologic CR except the following: 
 Platelet count $< 100 \times 10^9/L$ (100,000/μL)
Morphologic Leukemia-free State (MLFS)	Defined as less than 5% blasts in a BM aspirate sample with marrow spicules and with a count of at least 200 nucleated cells. There should be no blasts with Auer rods and absence of extramedullary disease
Partial Remission (PR)	Defined as all hematologic criteria of morphologic CR with a $> 50\%$ decrease in the percentage of BM blasts to 5% to 25% (a blast count value of $< 5\%$ may also be considered a partial remission if Auer rods are present) ^b
Cytogenetic Complete Remission (CRc)	Defined as CR/CRi/CRp with a reversion to a normal karyotype in cases with an abnormal karyotype at baseline, based on evaluating ≥ 20 metaphase cells from BM
Morphologic Relapse after CR/CRi/CRp^a	Defined as one of the following conditions: 
 Reappearance of $\geq 5\%$ blasts in the BM not attributable to any other cause (eg, BM regeneration after consolidation therapy); or Development of extramedullary disease
Not evaluable (NE)^a	Defined as without a post-treatment response assessment
Stable Disease (SD)^a	Defined as failure to meet any of the above criteria and not meeting the criteria of progressive disease (see below)

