Progressive Disease (PD)^a	Defined as one of the following conditions: 
 For subjects with 5 to 70% BM blasts at baseline: a $> 50\%$ increase of BM blast count percentage from baseline to $\geq 20\%$; or For subjects with $> 70\%$ BM blasts at baseline: a doubling of absolute blast count in PB from baseline to $\geq 10 \times 10^9/L$ (10,000/μL); or Development of new extramedullary disease since last response assessment 
Progressive disease is to be confirmed by 2 consecutive response assessments separated by at least 1 month. The date of progressive disease is defined as the first date that one of three conditions listed above was met.

AML = acute myeloid leukemia; ANC= absolute neutrophil count; BM= bone marrow; PB=peripheral blood;;IWG= International Working Group. CRh= morphologic complete remission with partial hematologic recovery: defined as less than 5% blasts in a BM aspirate sample with marrow spicules plus ANC $> 0.5 \times 10^9/L$ (1,000/ μ L) & Platelet count $> 50 \times 10^9/L$ (100,000/ μ L).

^a Modification to IWG response criteria.

^b If the pre-treatment BM blast percentage was 50% to 100%, the percentage of blasts must decrease to a value between 5% and 25%; if the pre-treatment blast percentage was 20% to less than 49%, they must decrease by at least half to a value of more than 5%.

Notes: Deletions to the IWG response criteria are not shown.

17.5. Hematologic Improvement According to the International Working Group for Myelodysplastic Syndromes

Hematologic Improvement According to IWG Criteria	
Hematologic improvement ^a	Response criteria (responses must last at least 8 week) ^b
Erythroid Response (HI-E) (pre-treatment, < 11 g/dL)	
 Hemoglobin increase by ≥ 1.5 g/dL Relevant Reduction in units of RBC transfusions by an absolute number of at least 4 RBC transfusions/8 week compared with the pretreatment transfusion number in the previous 8 weeks 
Note: Only RBC transfusions given for a hemoglobin of ≤ 9.0 g/dL on treatment will count in the RBC transfusion response evaluation^b

Platelet Response (HI-P) (pre-treatment, < $100 \times 10^9/L$)	
 Absolute increase of $\geq 30 \times 10^9/L$ for subjects starting with $> 20 \times 10^9/L$ platelets Increase from $< 20 \times 10^9/L$ to $> 20 \times 10^9/L$ and by at least 100%^b

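### Duration of response has no end event for loss of MLFS or PR, so it runs too long in responders who never reach CR, CRi or CRp

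*SAP*

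**What the plan says.** SAP 10.2.2 defines the endpoint: "Duration of response is defined as time from first documented CR/CRi/CRp/PR/MLFS to documented morphologic relapse, PD, or death due to any cause". Subjects with none of these events are censored at their last response assessment, whatever category it shows. Protocol 9.6.2 and Protocol Table 2 use the same start and end events.

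The end events take their meaning from SAP 17.4, and Protocol Appendix F matches it on relapse and PD:

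- **Relapse.** The row is titled "Morphologic Relapse after CR/CRi/CRp". It is met at 5% marrow blasts or by extramedullary disease. Nothing equivalent exists after MLFS or PR.
- **PD, marrow limb.** This applies "For subjects with 5 to 70% BM blasts at baseline" and needs an increase of more than half over baseline, to at least 20%.
- **PD, baseline above 70%.** There is no marrow limb. The criterion is "a doubling of absolute blast count in PB from baseline" to at least 10 x 10^9/L.
- **PD, any baseline.** "Development of new extramedullary disease since last response assessment".
- **Stable disease.** This is the residual row: "Defined as failure to meet any of the above criteria and not meeting the criteria of progressive disease".
- **PR range (footnote b).** For baselines of 50% to 100%, "the percentage of blasts must decrease to a value between 5% and 25" percent; for baselines of 20% to below 49%, "they must decrease by at least half to a value of more than 5" percent. PR also requires CR-level blood counts.

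PD must be confirmed at two consecutive assessments at least a month apart and is dated at the first. The note to SAP Table 4 treats any status other than relapse, PD or death as event-free.

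**The concern.** The DOR clock starts at five response categories, but loss of response is defined for only three of them. A subject with 50% blasts at baseline, 2% at MLFS and 60% later has lost the response by any ordinary reading, yet the criteria return stable disease. DOR then runs until PD, extramedullary disease or death, or is censored. The same marrow after CRi or CRp would have ended DOR at 5%.

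DOR also has no rule for new AML therapy. A subject who loses MLFS and switches treatment is censored rather than counted, because Protocol 3.1.2.4 stops response follow-up at second-line therapy. Protocol 7.2.1 mentions relapse following PR in its treatment text, but no criterion defines it, so investigators may record such cases differently.

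At stake is whether the reported median DOR describes time in response.

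**Working it through.** **Plan's own figure.** The documents give none for DOR or EFS. The only stated power is 75% for ORR (SAP 4.4: 50% v 30%, 66 v 33 subjects, two-sided 0.2). Unpooled SE = sqrt(0.3 x 0.7/33 + 0.5 x 0.5/66) = 0.1008; 0.2/0.1008 - 1.2816 = 0.703; power 75.9% (pooled 73.9%). It reproduces, and this point does not touch it.

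**Thresholds (documents only).** Entry requires at least 20% marrow blasts (Protocol 4.2). PD threshold = 1.5 x baseline. PR upper limit = the smaller of 25% and half of baseline.

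| Baseline blasts | PR upper limit | Marrow PD needs more than | Ratio to PR limit | Ratio to 5% |
|---|---|---|---|---|
| 20% | 10% | 30% | 3.0 | 6 |
| 30% | 15% | 45% | 3.0 | 9 |
| 40% | 20% | 60% | 3.0 | 12 |
| 50% | 25% | 75% | 3.0 | 15 |
| 60% | 25% | 90% | 3.6 | 18 |

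100/1.5 = 66.7, so from a 66.7% baseline the threshold is 100% or more (1.5 x 70 = 105%) and cannot be exceeded. Above 70% no marrow criterion exists.

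The stable-disease band runs from just above the PR limit (if counts are at CR level), or from 5% (if they are not), up to the PD threshold. Regrowth that still meets PR is a continuing response and is not part of the point.

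**Who is affected.** Only responders who never reach CR, CRi or CRp. The group need not be empty: CRi waives only the neutrophil limit and CRp only the platelet limit, so a cleared marrow with both counts low is MLFS.

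**Illustrative size (all inputs assumed).** Let true DOR be exponential with median m, and let a fraction w of responders have their end recorded D months late. Setting survival to one half gives

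median as written = m x {1 + log2[1 + w(2^(D/m) - 1)]}.

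- m = 6, w = 0.1, D = 2: 6 x {1 + log2(1.026)} = 6.22
- m = 6, w = 0.3, D = 6: 6 x {1 + log2(1.3)} = 8.27
- m = 12, w = 0.1, D = 2: 12.21
- m = 12, w = 0.3, D = 6: 14.03

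So the shift is about 0.2 to 2.3 months. For comparison, in a simulation with a true median of 9 months, 33 responders (66 x 50%) and censoring uniform over 12 to 30 months, the Kaplan-Meier median ranged over about 5.3 to 14.4 months (2.5th to 97.5th percentile).

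**EFS.** If 10 to 30% of responders are MLFS/PR-only in both arms, the affected share of all randomized subjects is 5 to 15% in the combination arm (50% ORR) and 3 to 9% in the azacitidine arm (30% ORR). With a true hazard ratio of 1, a 10-month median EFS, 24 months' follow-up and added delays of median 2 to 8 months, the simulated crude hazard ratio was 0.998 to 0.952.

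**The case against.** The strongest reply concerns scope. EFS is defined on relapse, progression or death, not on loss of response, and a subject who never responded is equally event-free with the same marrow. A reader might infer that EFS is simply wrong; its definition does not support that. The clear inconsistency is only that 5% blasts are an event after CRi or CRp but not after MLFS. A PR-based EFS event would create an anomaly: from a 60% baseline, a former PR at 26% would fail while a never-responder at up to 90% would not. This stands.

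A reader might also infer that nothing at all ends DOR in these subjects, or that the SAP and protocol criteria conflict. Neither holds. Death, extramedullary disease and PD still end it, including peripheral blast doubling when baseline is above 70%. The relapse and PD rows of SAP 17.4 and Appendix F match in substance.

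An unconfirmed loss event would itself be fragile: after PR from a baseline of 50% or more, one reading of 26% following 25% would end DOR. PD requires confirmation, and a loss rule should too.

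Finally, partial safeguards are planned: CR-only duration (SAP 10.2.3) and separate PR and MLFS counts (SAP 10.1). The protocol's amendment justification reports the primary-analysis CSR as final. These points lower the weight but leave the DOR gap open.

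**Conclusion.** The point holds for DOR in responders whose best response is MLFS or PR. Applied as written, the rule counts a lost response as continuing, so DOR is biased upward in that subgroup. The direction follows from the text; the size does not, because the documents give neither the MLFS/PR-only share nor the delay from loss of response to PD or death. The month figures are illustrations. They assume that every affected response is recorded late, even one ended by death, so the upper end is generous.

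ORR and its power, OS, CR-only duration and subjects who deepen to CR, CRi or CRp are unaffected. It would be tempting to conclude that equal MLFS/PR-only shares among responders remove any between-arm effect. For EFS they do not, since more responders are planned in the combination arm; but the possible drift is small, and the documents do not show that it occurs. This is a secondary-endpoint matter to consider.

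**What to change.** Change the endpoint derivation only; treatment and discontinuation rules stay as they are.

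1. **SAP 10.2.2.** Keep the current DOR and add a supplementary DOR. In it, after MLFS or PR, the end event also includes marrow blasts of 5% or more, not attributable to another cause, that meet no response category. The loss should be confirmed at a second consecutive assessment at least one month later, or followed by PD, death or new AML therapy, and dated at the first assessment. After PR, a fall in counts alone with blasts still in the PR range is not an event. Also report DOR restricted to CR/CRi/CRp responders.
2. **SAP 10.2.1, optional.** Add one EFS sensitivity analysis treating confirmed marrow blasts of 5% or more after MLFS as relapse. SAP 10.2.1 already allows further sensitivity rules. EFS2 does not cover this: it counts events after new therapy, not the regrowth. Do not add a PR-based EFS event.
3. **Limitation.** State that marrow PD cannot occur from a 66.7% baseline upward.
4. **Separate correction: CRh units.** SAP 10.2.11 and 17.4 equate 0.5 x 10^9/L with 1,000/uL (it is 500/uL) and 50 x 10^9/L with 100,000/uL (it is 50,000/uL); Appendix F prints an ANC limit of 500 x 10^9/L. Make them consistent, state which threshold was programmed, and apply the same confirmed-loss rule to CRh-only subjects in SAP 10.2.12.

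Label the additions post hoc for any reporting already finalized. The cost is SAP text and one derivation from marrow and blood values already collected (before Cycles 2, 3, 5 and every second cycle after). The downside is a second, somewhat shorter DOR to explain, with some sensitivity to marrow measurement noise.
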